APPENDIX B. HANDLING OF MISSING DATES

Partial dates will adhere to the following conventions in order to classify TEAEs and to classify prior and concomitant medications.

In general, listings will present the actual partial or missing values rather than the imputed values that may be used in derivation.

Adverse Events

In the event of a missing/incomplete start or stop date associated with an adverse event, only the treatment-emergence will be imputed using the algorithm below. Dates will not be imputed.

In general, if the missing/incomplete start date is not clearly prior to initiation of treatment, then the AE will be considered a TEAE.

If the AE end date is prior to the initiation of treatment, the AE will not be considered a TEAE.

If the AE end date is on or after the initiation of treatment:

- If the AE start date is completely missing or if the year is missing, then the AE will be considered a TEAE
- For partial AE start dates:
 - Known year, unknown month and day (or known year and day, unknown month)
 - If the year is the same as or later than the year of the first dose, the AE will be considered a TEAE
 - Otherwise, the AE will not be considered a TEAE
 - Known year and month, unknown day
 - If the month and year are the same as or later than the month and year of the first dose, the AE will be considered a TEAE
 - Otherwise, the AE will not be considered a TEAE

Prior and Concomitant Medications

No imputation process will be used to estimate missing data, except for the purposes of classifying medications as prior and/or concomitant. The following algorithms will be used for partially missing dates.

For start dates of medication uses:

- The day and month are missing: if the participant started receiving the study dosing in the reported year, the first dosing date will be used as the start date; otherwise '01 January' will be used as the start date.

- The day is missing: if the participant started receiving the study dosing in the reported month and year, the first dosing date will be used as the start date; otherwise, the first day of the reported month and year will be used as the start date.

[figure not shown]
For stop dates of events or medication uses:

- The day and month are missing: if the study end date is in the reported year, the study end date will be used as the stop date; otherwise, '31 December' will be used as the stop date.
- The day is missing: if the study end date is in the reported month and year, the study end date will be used as the stop date; otherwise, the end of the reported month and year will be used as the stop date.

If a medication has the stop date completely missing or missing the year, this medication will be considered as ongoing and concomitant. If a participant is missing a treatment start date, medication will not be classified as either prior or concomitant.

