13.7.6. Prior and Concomitant Medications

Medications will be recorded at each study visit during the study and will be coded using World Health Organization-Drug dictionary September 2015, or later.

All medications taken within 30 days prior to informed consent through the duration of the study will be recorded. Those medications taken prior to the initiation of the start of IP will be denoted “Prior”. Those medications taken prior to the initiation of the IP and continuing beyond the initiation of the IP or those medications started at the same time or after the initiation of the IP will be denoted “Concomitant”.

Medications will be presented according to whether they are “Prior” or “Concomitant” as defined above. If medication dates are incomplete and it is not clear whether the medication was concomitant, it will be assumed to be concomitant.

Details of prior and concomitant medications will be listed by participant, start date, and verbatim term.

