8.2.5. Prior and Concomitant Medications

Medications will be recorded at each study visit and coded into drug class (anatomical therapeutic chemical [ATC] Level 2) and PT using World Health Organization-Drug dictionary (WHO-DD) Global B3 March 2022, or later.

All medications taken within 30 days prior to informed consent through the duration of the study (including start and end dates, route, dose/units, frequency, and indication) will be recorded on the electronic case report form (eCRF).

Those medications taken prior to the initiation of the IP will be denoted “Prior”. Those medications taken prior to the initiation of the IP and continuing beyond the initiation of the IP or those medications started at the same time or after the initiation of the IP will be denoted “Concomitant”. Note that medication taken before the initial dosing of IP and continued after the initial dosing will be categorized as a prior medication and separately as a concomitant medication.

Medications will be flagged in the listing according to whether they are “Prior” or “Concomitant” as defined above. In the event of a missing start or stop date associated with a medication, only the classification (prior and/or concomitant) will be imputed using the algorithm described in [Appendix B](#). Dates will not be imputed.

Prior and concomitant medications will be summarized separately using the Safety Set as the number and percentage of participants with each medication at both the ATC and PT levels. Concomitant procedures will be listed with SOC/PT, but not summarized.

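### The SAP's partial-date rule for medications ignores a known stop date, so some drugs stopped before first dose are classed as Concomitant

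*SAP*

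**What the plan says.** SAP Appendix B (Handling of Missing Dates) has two branches for partial medication start dates.

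- Where only the day is absent, the rule reads: "if the participant started receiving the study dosing in the reported month and year, the first dosing date will be used as the start date". If the month or year differs from first dosing, "otherwise, the first day of the reported month and year will be used as the start date".
- Where day and month are both absent, it reads: "if the participant started receiving the study dosing in the reported year, the first dosing date will be used as the start date". If the year differs, 1 January is used.

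The appendix limits this step: nothing is imputed "except for the purposes of classifying medications as prior and/or concomitant". SAP 8.2.5 supplies the classes. A drug taken before the investigational product was begun is Prior. A drug begun earlier and carried on is both Prior and Concomitant, and "those medications started at the same time or after the initiation of the IP will be denoted" Concomitant. The two classes are tabulated separately on the Safety Set.

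Two other texts bear on the point. Protocol 13.7.6 says: "If medication dates are incomplete and it is not clear whether the medication was concomitant, it will be assumed to be concomitant". The adverse-event algorithm in SAP Appendix B opens with a test of the end date: "If the AE end date is prior to the initiation of treatment, the AE will not be considered a TEAE". SAP 6.1 declares no departure from the analyses in the protocol.

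**The concern.** The medication rule assigns a start without asking whether the drug had already stopped. The only stop-date sentence in Appendix B that decides a class covers a stop date that is wholly missing or has no year. A known stop before first dose is not addressed. For such a record with a partial start in the first-dose month or year, the rule produces an interval that starts after it ends, and SAP 8.2.5 then labels the drug Concomitant.

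That is a wrong result from a stated rule, not a conservative choice under uncertainty, because the stop date settles the question. What is at stake is the accuracy of the prior and concomitant medication tables. The protocol also requires certain drugs to be stopped before Day 1, for example primidone (9.2.2 and 9.2.3). A compliant pre-dose stop should not appear as use alongside SAGE-324.

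**Working it through.** The plan states no figure on this point, so there is none to reproduce. The check applies the Appendix B start rule and the SAP 8.2.5 definitions literally to test records.

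**Inputs.** The start rule and class definitions are from SAP Appendix B and 8.2.5. The dates are illustrative assumptions: first dose 20 June 2023, and stop 10 June 2023 where there is a stop.

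**Rule as coded.** Assigned start = first dose date if the reported month and year match (day missing) or the reported year matches (day and month missing). Otherwise it is the first of the month or 1 January. Prior if assigned start < first dose. Concomitant if assigned start ≥ first dose, or if assigned start < first dose and the drug continues to first dose or beyond.

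| Case | Recorded start | Stop | Assigned start | Class as written | Class with stop date tested first |
|---|---|---|---|---|---|
| A | Jun 2023 | 10 Jun 2023 | 20 Jun 2023 | Concomitant only | Prior only |
| B | 2023 | 10 Jun 2023 | 20 Jun 2023 | Concomitant only | Prior only |
| C | May 2023 | 10 Jun 2023 | 1 May 2023 | Prior only | Prior only |
| D | 2019 | 10 Jun 2023 | 1 Jan 2019 | Prior only | Prior only |
| E | 2 Jun 2023 | 10 Jun 2023 | 2 Jun 2023 | Prior only | Prior only |
| F | Jun 2023 | ongoing | 20 Jun 2023 | Concomitant only | Concomitant only |

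In A and B the assigned start is 20 − 10 = 10 days after the stop. C, D and E are classified correctly, so the failure is specific to the two branches that substitute the first dosing date. F is ambiguous, and Concomitant is what Protocol 13.7.6 prescribes.

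**Alternative reading.** If Prior is decided from the known stop date and not from the assigned start, A and B become both Prior and Concomitant. The Prior label survives, but the false Concomitant label remains.

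**When the error is possible.** Take a stop a fixed number of days before Day 1, and count the Day 1 dates in a 365-day year for which that stop falls in the same month (day-missing branch) or the same year (year-only branch).

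- 7-day gap, day missing: 365 − 12 × 7 = 281, and 281/365 = 77%.
- 7-day gap, year only: 365 − 7 = 358, and 358/365 = 98%.
- 14-day gap, day missing: 365 − 12 × 14 = 197, and 197/365 = 54%.
- 14-day gap, year only: 365 − 14 = 351, and 351/365 = 96%.

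These are calendar dates on which the error can occur. They are not the share of records affected, which also requires a partial start in that same month or year.

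**The case against.** The strongest reply is that the reach is narrow and the consequence small, and most of that stands.

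- **Drugs stopped for washout.** A reader might infer that primidone, CYP3A4 inhibitors or inducers, and estrogens stopped before Day 1 will generally be tabulated as concomitant. They will not. A drug with a recorded start in an earlier year or an earlier month stays Prior (cases C and D). The day-missing branch catches only a drug that both started and stopped in the first-dose month. The year-only branch needs a start in the first-dose year with no month recorded.
- **False protocol deviations.** A reader might also infer that a compliant stop would be counted as prohibited use. SAP 8.2.2 takes deviations from the eCRF and has the study team categorize them, so they do not derive from this flag. The visible list of displays has no table of prohibited medications and no analysis of adverse events by co-medication.
- **Loss from the Prior table.** This depends on the reading of SAP 8.2.5. It follows if the class is taken from the assigned start, but not if it is taken from the known stop.
- **Continuing drugs.** It is tempting to call it a second error that an ongoing drug with a same-month or year-only start loses Prior status. Its order relative to first dose is unknown, and classing it as Concomitant follows Protocol 13.7.6.
- **Imputing dates at all.** SAP 8.2.5 says "Dates will not be imputed", which might look like a contradiction of Appendix B. The preceding sentence in 8.2.5 and the opening of the Appendix B medication rule both confine imputation to classification, and listings show the actual partial dates.

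None of this removes the core defect. Under either reading, cases A and B are labelled Concomitant when the recorded stop shows that they were not.

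**Conclusion.** Wrong as written, minor severity. For a medication with a known stop before first dose and a partial start in the first-dose month (day missing) or first-dose year (day and month missing), the rule gives a start after the stop and a false Concomitant label. On a literal reading the Prior label is lost too. This conflicts with Protocol 13.7.6, since a known pre-dose stop makes the status clear, and it is out of step with the adverse-event rule in the same appendix.

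The number of affected records cannot be derived: the documents give no frequency of partial dates, and it could be close to zero. The effect is confined to Tables 14.1.7.1 and 14.1.7.2 and the flags in the medication listings, where the actual partial dates let a reader spot a wrong flag. The primary endpoint, incidence of treatment-emergent adverse events, is untouched. The conclusion rests on applying the Appendix B text literally; an unwritten stop-date check in the programming would avoid the error but would not be part of the plan.

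**What to change.** Add one sentence at the head of the medication rules in SAP Appendix B: *If the stop date (complete, or partial but clearly before first dose) precedes the first dose of IP, the medication is classified as Prior only; the start-date rules apply otherwise.*

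This turns cases A and B into Prior only and leaves C to F unchanged. It also settles the two readings of Prior for these records. The cost is one sentence and a small programming change before database lock, with no new data.

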APPENDIX C. LIST OF DISPLAYS

Display Number	Display Title	Analysis Set Used
Tables		
14.1.1	Disposition of Participants	All Participants
14.1.2	Analysis Sets	All Participants
14.1.3.1	Major Protocol Deviations	Safety Set
14.1.3.2	Protocol Deviations Related to COVID-19	Safety Set
14.1.4.1	Demographics and Baseline Characteristics	Safety Set
14.1.4.2	Demographics and Baseline Characteristics - Subgroups	Safety Set
14.1.5	Summary of Disease History	Safety Set
14.1.6	Medical/Surgical History	Safety Set
14.1.7.1	Prior Medications	Safety Set
14.1.7.2	Concomitant Medications	Safety Set
14.1.8.1	Investigational Product Exposure	Safety Set
14.1.8.2	Total Exposure Duration by Dose at Investigational Product Discontinuation	Safety Set
14.1.8.3	Investigational Product Adherence	Safety Set

[figure not shown]

14.3.1.1	Summary of Treatment-Emergent Adverse Events	Safety Set
14.3.1.2	Treatment-Emergent Adverse Events by System Organ Class and Preferred Term	Safety Set
14.3.1.3	Treatment-Emergent Adverse Events by Preferred Term	Safety Set

14.3.1.4	Serious Treatment-Emergent Adverse Events by System Organ Class and Preferred Term	Safety Set
14.3.1.5	Treatment-Emergent Adverse Events Leading to Investigational Product Discontinuation by System Organ Class and Preferred Term	Safety Set
14.3.1.6	Treatment-Emergent Adverse Events Leading to Study Discontinuation by System Organ Class and Preferred Term	Safety Set
14.3.1.7	Treatment-Emergent Adverse Events by Maximum Severity	Safety Set
14.3.1.8	Treatment-Emergent Adverse Events by Maximum Relationship to Investigational Product	Safety Set
14.3.1.9	Serious Treatment-Emergent Adverse Events by Preferred Term	Safety Set
14.3.4.1.1	Summary of Clinical Chemistry	Safety Set
14.3.4.1.2	Shift of Clinical Chemistry	Safety Set
14.3.4.1.3	Potentially Clinically Significant (PCS) Values in Clinical Chemistry Excluding Liver Function Tests	Safety Set
14.3.4.1.4	Potentially Clinically Significant (PCS) Values in Liver Function Tests Any Time Post-baseline	Safety Set
14.3.4.2.1	Summary of Hematology	Safety Set
14.3.4.2.2	Shift of Hematology	Safety Set
14.3.4.2.3	Potentially Clinically Significant (PCS) Values in Hematology	Safety Set
14.3.4.3.1	Summary of Coagulation	Safety Set
14.3.4.3.2	Shift of Coagulation	Safety Set

14.3.4.3.3	Potentially Clinically Significant (PCS) Values in Coagulation	Safety Set
14.3.4.4.1.1	Summary of Urinalysis, Continuous Parameters	Safety Set
14.3.4.4.1.2	Summary of Urinalysis, Categorical Parameters	Safety Set
14.3.4.4.2	Shift of Urinalysis	Safety Set
14.3.4.5.1	Summary of 12-Lead Electrocardiogram	Safety Set
14.3.4.5.2	Shift of Overall Electrocardiogram Interpretation	Safety Set
14.3.4.5.3	Potentially Clinically Significant (PCS) QTcF Values	Safety Set
14.3.4.6.1	Summary of Vital Signs	Safety Set
14.3.4.6.2	Potentially Clinically Significant (PCS) Values in Vital Signs	Safety Set
14.3.4.7.1	Summary of Columbia-Suicide Severity Rating Scale	Safety Set
14.3.4.7.2	Shift From Baseline in Columbia-Suicide Severity Rating Scale (C-SSRS) Suicidal Ideation and Suicidal Behavior by Study Visit	Safety Set
14.3.4.7.3	Shift From Baseline in Columbia-Suicide Severity Rating Scale (C-SSRS) Maximum Severity Score in Suicidal Ideation at Any Time Post-baseline	Safety Set
14.3.4.8	Summary of Physician Withdrawal Checklist (PWC-20)	Safety Set
14.3.4.9.1	Summary of Epworth Sleepiness Scale – Individual Items	Safety Set
14.3.4.9.2	Summary of Epworth Sleepiness Scale – Total Score	Safety Set

Listings		
16.2.1.1	Participant Disposition	All Participants
16.2.1.2	Screen Failures	Screen Failure Participants
16.2.2.1	Inclusion/Exclusion Criteria Violations	All Participants, Excluding Screen Failures
16.2.2.2	Protocol Deviations	Safety Set
16.2.3	Analysis Sets	All Participants
16.2.4.1	Demographics and Informed Consent	Safety Set
16.2.4.2	Child-bearing Potential	Safety Set
16.2.4.3.1	Medical/Surgical History	Safety Set
16.2.4.3.2	Essential Tremor Disease History	Safety Set
16.2.4.4.1	Prior Medications	Safety Set
16.2.4.4.2	Concomitant Medications	Safety Set
16.2.4.5	Concomitant Procedures	Safety Set
16.2.5.1	Investigational Product Dispensation and Return	Safety Set
16.2.5.2.1	Investigational Product Administration – Daily Dosing Diary	Safety Set
16.2.5.2.2	Investigational Product Administration – Log Records	Safety Set
16.2.5.3	Investigational Product Exposure and Adherence	Safety Set
51		

16.2.7.1	Adverse Events	Safety Set
16.2.7.2	Serious Adverse Events	Safety Set
16.2.7.3	Deaths	Safety Set
16.2.7.4	Adverse Events Leading to Investigational Product Discontinuation	Safety Set
16.2.7.5	Adverse Events Leading to Study Discontinuation	Safety Set
16.2.8.1.1	Clinical Chemistry	Safety Set
16.2.8.1.2	Clinical Hematology	Safety Set
16.2.8.1.3	Clinical Coagulation	Safety Set
16.2.8.1.4	Urinalysis	Safety Set
16.2.8.2.1	Pregnancy Test	Safety Set
16.2.8.2.2	FSH Testing	Safety Set
16.2.8.2.3	Local Drug Screen	Safety Set
